8.1 Preparation of PRP

Autologous Platelet-Rich Plasma (PRP) is prepared by taking 120 mL aliquots of anticoagulated peripheral blood (120 mL whole blood and 16 mL anticoagulant citrate dextrose formula A) obtained from each subject by venipuncture. Each aliquot is processed by an autologous platelet separator (Arthrex Angel, Arthrex Inc., Naples, Florida) to yield 3-10 mL of PRP from each subject. Platelet poor plasma (PPP) can be added to PRP to achieve the desired injection volume. This system is FDA approved by 510(k) for "clinical laboratory or intraoperatively at the point of care for the safe and rapid preparation of platelet poor plasma and platelet concentrate (platelet rich plasma) from a small sample of whole blood or a small mixture of blood and bone marrow". For participants randomized to the control arm, blood will still be drawn but will not be processed to make PRP.

8.2 Administration of Investigational Therapies

8.2.1 Platelet-Rich Plasma

The patient will be positioned supine. A sterile field will be developed with Betadine prep of the genitalia, sterile gloves and a sterile extremity drape. A total of 20 mL of 1% lidocaine will be drawn up using an 18-gauge needle and will be subcutaneously administered using a 27-gauge needle into the subcutaneous tissue at the base of the penis to obtain a dorsal nerve block. A 1/4inch Penrose drain will be used as a tourniquet by placing it at the base of the penis and maintaining it in place under tension by a sterile clamp. A maximum of 5 mL of PRP will be infused steadily over a two-minute period – approximately 2.5 mL each into the right and left

corpus cavernosum, as shown in Figure 1. The injections will be performed at this slow speed (each side over 2 minutes of infusion) to minimize injury to the platelet cells. In the control arm, men will be administered injectable normal saline that will be injected in a similar manner as the PRP.

Following administration of PRP or normal saline, compression of the penis will be achieved with a clenched fist for 20 minutes. At 20 minutes, the tourniquet will be removed, and a compressive dressing will be placed around the penile shaft. The patient will be instructed to remove the compression bandage in 4 hours and to contact the study coordinators if he experiences any problems.

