****CONFIDENTIAL & PROPRIETARY****

List of Abbreviations and Definition of Terms

AE	Adverse Events
BPH	Benign Prostatic Hyperplasia
BRB	Biomedical Research Building
CNS	Central Nervous System
CRF	Case Report Form
CTCAE	Common Terminology Criteria for Adverse Events
eCRF	Electronic Case Report Form
ED	Erectile Dysfunction
EDITS	Erectile Dysfunction Inventory of Treatment Satisfaction
EDV	End Diastolic Velocity
GCP	Good Clinical Practice
HIPAA	Health Information Portability and Accountability Act
ICF	Informed Consent Form
ICH	International Conference of Harmonization
ICI	Intracavernosal Injection
IEC	Institutional Ethics Committee
IIEF	International Index of Erectile Function
IIEF-EF	Erectile Function Subdomain Score
IRB	Institutional Review Board
ISCI	Interdisciplinary Stem Cell Institute
MCID	Minimal Clinically Important Difference
mL	Milliliter
ng/dL	Nanograms Per Deciliter
PDE5i	Phosphodiesterase 5 inhibitor
PPP	Platelet Poor Plasma
PRFM	Platelet Rich Fibrin Matrix
PRP	Platelet Rich Plasma
PSV	Peak Systolic Velocity
RCT	Randomized Controlled Trial
SAE	Serious Adverse Events
SEP3	Sexual Encounter Profile
SOP	Standard Operating Procedure
SWT	Low-intensity Shockwave Therapy
TE-SAE	Treatment Emergent Serious Adverse Events
UM	University of Miami
VAS	Visual Analogue Pain Scale

Protocol Synopsis						
TITLE	COMBINING SHOCKWAVE THERAPY AND PLATELET RICH PLASMA FOR TREATING ERECTILE DYSFUNCTION IN DIABETIC MEN (COCKTAIL-DM)					
SPONSOR	Jniversity of Miami, Miller School of Medicine - Department of Urology					
PHASE OF STUDY	Phase I/II					
STUDY THERAPY	Autologous Platelet-Rich Plasma (PRP) + Low-intensity Shockwave Therapy (SWT)					
STUDY DESIGN	Single arm, Open Label, Pilot Trial					
ROUTE OF ADMINISTRATION	Intracavernosal Injection (PRP) + extracorporeal shockwave therapy (SWT)					
SUBJECT POPULATION	15 male subjects between the age of 30-80 with Mild or Mild-to-Moderate ED and controlled Diabetes Mellitus (DM)					
STUDY	Primary: To investigate biochemical markers of neo-angiogenesis in patients before and after PRP injection + SWT					
OBJECTIVES	Secondary: To study efficacy and incidence of adverse events and safety of PRP injection + SWT treatment in men with mild-moderate ED, as measured by IIEF.					
	15 men with Erectile Dysfunction (ED) of organic origin and Diabetes (Type 1 or Type 2), that meet all of the inclusion and none of the exclusion criteria, will be enrolled and will receive PRP+SWT.					

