- 7.2.10 Endothelial Progenitor Cell Colony Forming Units (EPC-CFUs): Peripheral blood samples will be collected from participants for isolation of EPCs using Ficoll-Paque density gradient. Plasma will be aliquoted and stored for future analysis. Five million cells will be seeded on 6-well Fibronectin-coated dishes (BD Biosciences) in CFU-Hill medium (Stem Cell Technologies, cat#05900)4 and incubated at 37°C in humidified 5% CO2. Non-adherent cells will be collected after 48 hours, and 1 million cells will be seeded on 24-well Fibronectin-coated dishes. On day 5, EPC-CFUs will be counted in 6 wells and the average will be obtained.
- **7.2.11** Brachial Artery Flow Mediated Dilation (FMD): FMD% is a non-clinical measure; it is a tool used specifically for research to obtain an understanding the functionality of the vascular endothelium. 2D ultrasound will be used to measure Flow Mediated

Diameter percent change (FMD%). All measurements of the brachial artery diameter and FMD% will be performed in the morning, in a quiet and dark room and at controlled ambient temperature. Subjects will fast overnight and refrain from consuming caffeine, nicotine, or other stimulants for at least 8 hours prior to ultrasound and should refrain from vigorous exercise for at least 4 hours prior to ultrasound. Subjects are permitted to drink water and take medications (except PDE5 inhibitors) as usual. The subject will rest for 10 minutes in the supine position prior to scan. The subject's right arm will be comfortably immobilized in an extending position, allowing for ultrasound scanning of the brachial artery 5–10 cm above the antecubital fossa. In each examination, recording of vessel images will be followed by inflation of a cuff to supra-systolic pressure (40 to 50 mmHg above systolic pressure) for 5 minutes. Then the cuff will be deflated, and the brachial artery diameter will be imaged and recorded for 3 minutes.

- **7.2.12** *Platelet-Rich Plasma (PRP) Injection*: Approximately 120mL of blood will be collected from participants for preparation of investigational product. Refer to Section 8 for description of Investigational Product (IP) preparation and administration.

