7.3 Description of Study Visits

7.3.1 Screening Visit

Visit 1 (0 – 28 days before therapy): The basic work-up will take place, including medical and sexual history, as well as necessary lab tests (testosterone, prolactin, hematology, chemistry), if not available during the last 12 months prior to screening. Subjects will complete the IIEF questionnaire. We will ensure that patients have 4 attempts for intercourse Screening visit can occur on same day as first injection + SWT. Refer to table 1 for procedures to be performed at the Screening visit.

7.3.2 Treatment Visits: Week 0 – Week 4

Upon evaluation of eligibility, subjects will be randomized to one of the two parallel study groups using an online program, and initiate treatment on the same day.

There will be 5 treatment visits for all groups, each occurring at weekly intervals (\pm 2 days), for a total duration of five weeks. Subjects will complete a Visual Analogue Scale (VAS) pain score after the end of each treatment. Refer to table 1 for all procedures to be performed at the treatment visits.

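### The synopsis and section 7 give PRP+SWT to all 15 men in one open-label arm, but other sections randomise men to a saline control arm, and section 12.1 compares treatment with control

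*Combined protocol and SAP*

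**What the plan says.** **One arm.** The synopsis gives the design as "Single arm, Open Label, Pilot Trial" and says that the 15 men "will be enrolled and will receive PRP+SWT". Section 7 again assigns all 15 to PRP+SWT, open label, and section 5 also describes an open-label pilot. The primary objective in the synopsis is to study markers of neo-angiogenesis before and after the combined treatment. Section 2.1 words it more broadly, as the mechanisms of PRP and SWT.

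**Two arms.**
- Section 7.3.2: once eligible, "subjects will be randomized to one of the two parallel study groups using an online program, and initiate treatment on the same day". It continues: "There will be 5 treatment visits for all groups, each occurring at weekly intervals".
- Section 8.1: "For participants randomized to the control arm, blood will still be drawn but will not be processed to make PRP".
- Section 8.2.1: "In the control arm, men will be administered injectable normal saline that will be injected in a similar manner as the PRP". The next paragraph repeats the alternative: "Following administration of PRP or normal saline, compression of the penis will be achieved".
- Section 12.1: repeated-measures ANOVA or Student's t-test for continuous data, with the stated purpose of comparing treatment and control groups, and Fisher's exact test for categorical differences between groups, at α = 0.05.
- Matching wording stands in the header of the schedule of events (section 7.1), which counts screening back from randomisation; in section 7.2.13, which speaks of randomised patients in a treatment group; and in section 13.2, which describes benefit for men randomised to the treatment arm.

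**The concern.** These are current, operative sections, and they describe two different trials. The investigators undertake in section 15.2 to follow the protocol, and they cannot follow both versions.

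Two things are at stake. The first is the analysis. Section 12.1 is the only statement of how the data will be tested, and it is written for two groups. If the trial has one, the plan does not say how change from baseline will be assessed. The second is conduct. Sections 8.1 and 8.2.1 are the working instructions for preparing and giving the injection. Read on their own, they tell staff to leave some men's blood unprocessed and to inject saline.

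**Working it through.** The plan gives no power calculation, effect size, SD or derivation of the 15, so there is no figure to reproduce. The check is textual, followed by a test of whether section 12.1 can be run under the stated design.

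**1. Side by side**

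| Question | Synopsis and section 7 | Other sections |
|---|---|---|
| Number of groups | One (the term itself is only in the synopsis) | Two (7.3.2) |
| Who gets PRP | All 15 | Not the control arm (8.1, 8.2.1) |
| Who gets saline | Nobody: 0 of 15 | The control arm (8.2.1); number not derivable |
| Randomisation | None mentioned | Online program (7.3.2); also the schedule header, 7.2.13, 13.2 |
| Allocation ratio, arm size, blinding | Not needed | Not given anywhere |
| Comparison | Before and after (synopsis objective) | Treatment with control (12.1) |

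The two-arm wording stands in seven places: 7.3.2, 8.1, 8.2.1, 12.1, the schedule header, 7.2.13 and 13.2. Saline is named only in 8.2.1; section 8.1 refers to the control arm without saying what it receives.

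**2. Can section 12.1 be run with one arm of 15?**
- *Fisher's exact test.* With 15 treated and 0 control men, of whom x have the event, the only table with those margins has probability C(15,x)·C(0,0)/C(15,x) = 1. So p = 1 whatever the data show.
- *Two-sample t-test.* The standard error contains 1/n for the control group. With n = 0 it is undefined.
- *Repeated-measures ANOVA.* This can be run with visit as the within-subject factor. EPC-CFUs, for example, are scheduled at screening, Month 3 and Month 6. With 15 complete cases, the visit effect has 3 − 1 = 2 and (15 − 1)(3 − 1) = 28 degrees of freedom. That tests change over time. It cannot serve the purpose that 12.1 gives it, because there is no group factor.

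So one named method survives, but its stated purpose is wrong for a single arm.

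**3. Illustration only: why the choice of design matters.** Assume two-sided α = 0.05 (sidedness is not stated), 80% power and, for two arms, a split of 8 and 7 (no split is stated). From the noncentral t distribution:
- One arm, paired test: noncentrality d√15 on 14 df, giving d ≈ 0.78 SD of the within-man differences.
- Two arms: noncentrality d√(8·7/15) on 13 df, giving d ≈ 1.57 SD.

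The two SDs are different quantities, so the values of d are not directly interchangeable. The conclusion does not rest on this step.

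**The case against.** The best reply is that the control-arm text is residual wording. There is one site, the synopsis and section 7 agree that all 15 men receive PRP+SWT, and a two-arm trial could not be run from this text without a ratio, arm size or blinding plan. Open label is also no contradiction in itself, since an open-label trial can be randomised. And repeated-measures ANOVA is usable in one arm.

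Much of this stands. It makes saline exposure a risk of literal reading rather than the main consequence. It also means that a reader should not infer that the primary objective has no usable method: the method is there, with the wrong purpose attached. What the reply does not do is repair section 12.1, or point to any passage that says the control text no longer applies.

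Other inferences that a reader might draw go too far:
- *That control men would get no shockwave therapy.* Section 7.2.13 says what the treatment group receives and is silent on controls. Section 8.2.2 gives SWT to every subject, and the two can stand together.
- *That section 8.2.2 fixes the total at 3,600 shocks.* That total is in the synopsis, section 7 and 7.2.13. Section 8.2.2 gives sessions and shocks per session only.
- *That a volume of wasted blood can be computed* from the 120 mL in section 8.1 and two injection visits. No control-arm volume is stated.
- *That particular endpoints depend on Fisher's test.* Section 12.1 assigns no test to any named endpoint.
- *That the men have been misinformed.* The consent form is not available here, so this cannot be judged.

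**Conclusion.** The conflict is real and needs correcting. Under the stated single-arm design, the purpose given for the section 12.1 analysis and its between-group Fisher's test have no comparator. The before-and-after objective in the synopsis is therefore not what section 12.1 says it will test. This follows from the text and needs no assumption beyond taking the synopsis design as the intended one. The point about the objective is limited to the synopsis wording, because section 2.1 is broader.

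The secondary risk is an unused blood draw and a saline injection in men whom the synopsis and section 7 assign to PRP+SWT. Its size cannot be given without an allocation ratio or arm size. The choice of a single arm for a pilot is not criticised.

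**What to change.** If one arm is intended, as the synopsis says:
- **7.3.2:** delete the randomisation wording and the reference to all groups.
- **8.1:** delete the control-arm sentence.
- **8.2.1:** delete the saline sentence and the mention of saline in the paragraph on compression.
- **Schedule of events header (7.1):** count screening as *before first treatment*.
- **7.2.13:** open with *All subjects* in place of the randomised treatment group.
- **13.2:** refer to *participants*.
- **12.1:** for continuous outcomes measured at baseline and follow-up, state the aim as within-subject change from baseline, by repeated-measures ANOVA or paired t-test. Report categorical outcomes as single-group proportions with confidence intervals, in place of the between-group Fisher's test.

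The cost is a protocol amendment with IRB approval, for which section 15.2 already provides, including a short rewrite of 12.1. It adds no patients and no procedures.

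If a control arm is in fact intended, the synopsis and sections 5 and 7 must instead state the arms, the number in each, the allocation and the blinding, and whether controls receive SWT. That is a larger change, because the 15 men would then be divided between two groups.

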8.2.2 Low Intensity Shockwave Therapy

Figure 2 shows the MoreNova device, which is a Linear Shockwave (LISW) transducer capable of delivering shockwaves to a treatment region confined to a narrow rectangle. Shockwaves generation follows the electromagnetic principle. Linear Shockwaves (LISW) has been under evaluation, as a treatment for ED for the last five years. The present study will utilize a device called "MoreNova", in which shockwaves are focused onto line segments for improved organ coverage. Shockwaves produced by "MoreNova" are aimed at the left and right corpora cavernosa and the crura. The study is aimed at determining the safety

Tigure 2. Morenova SVT Device

and efficacy of this new type of LISW in the treatment of ED. The treatment session lasts approximately 20 minutes and may be performed in an office environment. Treatment is applied in the physician's office.

All subjects will receive 5 weekly sessions, in which 720 shocks of treatment energy will be applied in every session to each treated region (left and right corpora cavernosa and crura).

9. Data Management

Data will be entered from source documents into eCRFs which are maintained in an online research database. The investigator will ensure data integrity by confirming the CRF's are attributable, legible, contemporaneous, original, accurate, and complete.

9.1 Case Report Forms (CRFs)

The Investigator or designee must record all required subject data, and an explanation must be documented for any missing data. This study will use electronic case report forms (eCRF) for data entry and database storage.

9.2 Source Documents

Source data is all information, original records of clinical findings, observations, or other activities in a clinical trial necessary for the reconstruction and evaluation of the trial. Source data are contained in source documents. Examples of these original documents, and data records include: hospital records, clinical and office charts, laboratory notes, memoranda, subjects' diaries or evaluation checklists, recorded data from automated instruments, copies or transcriptions certified after verification as being accurate and complete, and records kept at medical technical departments involved in the clinical trial. All corrections to study data will be made by drawing a single line through the information to be corrected without obscuring it. All corrections will be initialed, dated and explained, if necessary, in accordance with good clinical practice (GCP) guidelines.

9.3 Study Monitoring, Auditing, and Inspecting

The investigator will permit study-related monitoring, audits, and inspections by the IRB, government regulatory bodies, and University compliance and quality assurance groups of all study related documents. The investigator will ensure the capability for inspections of applicable study-related facilities.

10. Data and Specimen Banking

10.1 Storage of Data

Data will be maintained on research team hardware, and subject charts will be stored in a filing room maintained by Department of Urology. Clinical follow up and laboratory data will be stored in a locked room, with access only to authorized personnel. It is up to the principal investigator's discretion as to how long non-FDA study essential documents are retained.

10.2 Specimen Banking

Bio-specimens will be reserved for future testing and stored at -80 degrees Celsius in equipment maintained by ISCI in the Biomedical Research Building (BRB) (address: [name]). Each specimen must have a corresponding requisition form to track the chain of custody from time of collection to time of processing and/or storage.

11. Safety Monitoring and Reporting

11.1 Adverse Events (AEs)

An adverse event (AE) is defined as any untoward medical occurrence associated with the use of a drug in humans, whether or not considered drug related. An AE can be any unfavorable and unintended sign (including an abnormal laboratory finding), symptom, or disease temporally associated with the study. The event does not need to have a causal relationship with treatment. Common Terminology Criteria for Adverse Events Version 5 (CTCAE) will be used for describing AEs. All urological and/or reproductive system AEs will be recorded. For all other AEs, only events greater than grade 2 will be recorded.

Based on our own pilot data assessing SWT and PRP monotherapy, we have compiled the following data on adverse events (Table 2):

We anticipate there to be few adverse events related to the study. Based on the four published studies and abstracts, including 75 men, only minor adverse events were reported (Bruising 1, Mild Pain 4). No serious adverse events were observed [23-26].

SWT related adverse events	
Transient mild cutaneous purpura	0.10%
Local erythema	0.50%
Local swelling/edema	1.00%
Transient local anesthesia or paranesthesia	1.10%
Transient local anestnesia of paranestnesia	1.10/0

PPR related adverse events					
Pain greater than 5/10 at time of injection	5.00%				
Pain lasting > 5 days	5.00%				
Penile bruising	0.00%				
Penile fracture	0.00%				

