11.1.1 Expectedness

An adverse event is considered "unexpected" if it is not listed in the investigator brochure, protocol, ICF, or is not listed at the specificity or severity that has been observed; or, if an investigator brochure is not required or available, is not consistent with the risk information described in the general investigational plan or elsewhere in the current application.

Anticipated adverse events for this study include: Pain, Bruising, Swelling, Edema, Allergy, Penile Fracture, and/or New Penile Curvature.

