11.1.2 Severity

Common Terminology Criteria for Adverse Events, Version 5 (CTCAE v5.0) will be used to assess severity of adverse events. All grade 3-5 adverse events, regardless of association with the investigational therapy, will be entered into study database and reviewed at research committee meetings.

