13.1 Risks to Subjects

We anticipate there to be few adverse events related to the study. Based on the four published studies and abstracts, including 75 men, only minor adverse events were reported (Bruising 1, Mild Pain 4). No serious adverse events were observed [23-26]. After literature review, we believe this product to be of non-significant risk to patients (NSR) and for investigational use in a clinical study protocol.

Based on published studies, we will record anticipated adverse events to patients include: local injection site reaction, penile pain, penile hematoma (bleeding into the tissue), penile swelling, allergic reaction to the anesthetic, local infection, penile fracture, or new penile curvature. In addition, there may be uncommon or previously unknown risks that might occur. We will record every adverse event at every visit systematically.

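### Sections 11.1 and 13.1 give incompatible rules for recording adverse events; under 11.1 a grade 1-2 allergic reaction, which the protocol anticipates, would go unrecorded

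*Combined protocol and SAP*

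**What the plan says.** Section 11.1 (Adverse Events) defines an adverse event broadly, without requiring a causal link, and then sets a two-part recording rule. For the treated organ system: "All urological and/or reproductive system AEs will be recorded". For everything else: "For all other AEs, only events greater than grade 2 will be recorded".

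Section 11.1.2 (Severity) adds a database rule: "All grade 3-5 adverse events, regardless of association with the investigational therapy, will be entered into study database". It does not mention grades 1 and 2.

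Section 13.1 (Risks to Subjects) states that anticipated events will be recorded, with a list that includes "penile swelling, allergic reaction to the anesthetic, local infection, penile fracture, or new penile curvature". It warns that unknown risks may also appear, and then says: "We will record every adverse event at every visit systematically". No limit by grade or body system is attached.

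Section 11.1.1 (Expectedness) has its own list: "Anticipated adverse events for this study include: Pain, Bruising, Swelling, Edema, Allergy, Penile Fracture, and/or New Penile Curvature".

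The synopsis gives the secondary objective as "To study efficacy and incidence of adverse events and safety of PRP injection + SWT treatment". Section 2.2 words that objective more generally, as safety and efficacy. The only safety endpoint listed in section 3.2 is the incidence of serious adverse events up to 6 months.

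**The concern.** For any grade 1-2 event outside the urological and reproductive systems, site staff must break one of the two rules. Which rule they break decides whether the event exists in the data.

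If 11.1 is followed, the filter applies whether or not the event is anticipated and whether or not it is attributed to treatment. A moderate allergic reaction judged to be caused by a study procedure would be dropped on the same terms as an unrelated cold. In a Phase I/II study of a combination, with a single arm and 15 men, no comparison group or later analysis can recover what was not written down. A zero in the final table would look like an observation when it is only a product of the recording rule.

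**Working it through.** The plan states no figure on this point, so there is nothing to reproduce. The main check sets the sections side by side.

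**Step 1: do the rules conflict?**

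| Event | 11.1 | 11.1.2 | 13.1 |
|---|---|---|---|
| Urological/reproductive, any grade | recorded | database entry required for grades 3-5; silent on 1-2 | recorded |
| Other system, grade 3-5 | recorded | database entry required | recorded |
| Other system, grade 1-2 | not recorded | silent | recorded |

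The conflict is confined to the last row. Sections 11.1 and 13.1 both speak of recording, so they cannot be reconciled by assigning one to source notes and the other to the database. Section 11.1.2 does not settle the row because it says nothing about these grades.

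**Step 2: which anticipated events fall in the last row?**

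- Certainly: allergy (11.1.1), which appears as an allergic reaction to the anesthetic in 13.1.
- Possibly: local infection and injection site reaction (13.1), and the purpura, erythema, swelling and transient sensory loss listed for shockwave therapy in Table 2 of 11.1. These occur at the treated site but could be classed as skin, nervous system or infection events. The protocol gives no rule.
- Not lost: penile pain, hematoma, swelling, fracture and curvature, which 11.1 keeps at every grade.

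**Step 3: how many events might be involved?**

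The documents give no rate for non-urological grade 1-2 events, so p below is an assumption. The value 1.1% borrows the highest shockwave rate in Table 2 (a local sensory event). The value 5% equals the PRP pain rates in the same table, although penile pain is exempt from the filter. The value 10% is purely illustrative. Table 2 does not say whether its rates are per man or per session; p is treated here as per man, independent across n = 15.

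P(at least one) = 1 - (1 - p)^15; expected men affected = 15p.

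| Assumed p | P(at least one of 15) | Expected men | Recorded under 11.1 |
|---|---|---|---|
| 1.1% | 1 - 0.989^15 = 15.3% | 0.165 | 0 |
| 5% | 1 - 0.95^15 = 53.7% | 0.75 | 0 |
| 10% | 1 - 0.90^15 = 79.4% | 1.5 | 0 |

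**Step 4: what would a zero mean?**

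With full recording, 0 of 15 still allows a true rate of up to 1 - 0.05^(1/15) = 18.1% (one-sided 95% bound), or 1 - 0.025^(1/15) = 21.8% (upper limit of the two-sided 95% interval). Under 11.1 even that weak statement is unavailable, because the count is zero at any true rate.

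**The case against.** The best defence has four parts.

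First, limiting collection of low-grade events outside the target organ can be a legitimate choice in a small pilot, and 11.1 keeps what matters most locally. That stands as a general point, but this protocol also promises full recording, so the choice is not actually made.

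Second, 13.1 says that anticipated events will be recorded and names the allergic reaction. That could be read as an exception to 11.1. It shows intent, but 11.1 contains no exception, and the sentence in 13.1 promising every event remains in conflict on any reading.

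Third, the listed safety endpoint is serious adverse events, which section 11.2 defines by outcome rather than grade, and 11.1.2 captures all grade 3-5 events. This stands. Pain is also scored on the VAS at all five treatment visits.

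Fourth, no document rate supports a large number of missed events. This also stands.

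Stronger readings are therefore tempting but unsupported. A reader might infer that most anticipated events would be lost; only allergy certainly is. A reader might count mild reactions to the roughly 120 mL blood draw as anticipated events; they would be filtered, but neither list names them. A reader might expect a published statement that only local events occur; no section plans one.

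**Conclusion.** The contradiction between 11.1 and 13.1 is real and nothing elsewhere in the protocol resolves it. If 11.1 governs, grade 1-2 allergic reactions are certainly unrecorded, and local skin, sensory or infection events are recorded or not according to a classification left to the site. Adverse event incidence, as worded in the synopsis secondary objective, is then understated.

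A reader might infer that the trial's safety endpoint is compromised. The documents do not support that: serious adverse event incidence is largely untouched. Nor are the 15%, 54% and 79% figures estimates of what this trial will miss. They rest on assumed per-man rates and show only that such an event among 15 men could be anything from unlikely to likely. This should be corrected before enrolment; it does not call the design into question.

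**What to change.** Reconcile 11.1, 11.1.2 and 13.1 into one rule. The simplest way is to delete the grade filter in 11.1 so that it matches 13.1: record all adverse events, any body system and any CTCAE grade, from first treatment to Month 6. Section 11.1.2 can continue to direct grade 3-5 events to the research committee.

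If the sponsor prefers to keep a filter for unrelated events, 11.1 should exempt all anticipated and treatment-related events at every grade and say how local skin, sensory and infection events are classified. The sentence in 13.1 that promises every event should then be corrected.

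The first option costs one deleted sentence and slightly more data entry for 15 men. The Schedule of Events already reviews adverse events at seven visits (five treatment, two follow-up), so no visit or procedure is added. The second option saves some entry but requires a relatedness judgement before an event is recorded, which in an open-label study is itself a source of bias.
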